Rituximab 375 mg/m² will be given on Day 1 and Day 2 of Cycle 1 and Day 1 of Cycles 2 and 3. Ifosfamide will be administered via continuous infusion over 24 hours at a dose of 5000 mg/m² on Day 3 of each cycle. Carboplatin will be administered on Day 3 as a dose of AUC = 5 mg/mL. Etoposide 100 mg/m² will be given IV on Days 3 to 5.

As an alternate to the Protocol-specified dose and dose schedule, R-ICE may be administered according to institutional practice with medical monitor approval.

Duration of Participation:

Subjects will be treated until withdrawn from the study. This may occur due to toxicity, disease progression, refusal to continue, the subject becomes eligible for a stem cell transplant or investigator, sponsor, or regulatory authority decision to terminate the study or institute a clinical hold. Subjects who have evidence of objective clinical benefit, regardless of dose level, may continue to be treated at that dose level.

Subjects enrolled onto INCB050465 monotherapy have the option of crossing over to combination therapy upon progressive disease at the discretion of the investigator if a combination cohort is currently enrolling.

The average duration of participation is expected to be approximately 6 months.

Study Population:

Individuals diagnosed with B-cell malignancies (except Burkitt's lymphoma and precursor B-lymphoblastic leukemia/lymphoma) or HL who have failed or are refractory to available treatments.

Key Inclusion Criteria:

- Aged 18 years or older with lymphoid malignancies of B-cell origin including the following:
 - Indolent / aggressive B-cell non-Hodgkin's lymphoma (NHL)
 - EXCLUDING: Burkitt's lymphoma and precursor B-lymphoblastic leukemia/lymphoma
 - INCLUDING: any non-Hodgkin's B-cell malignancy such as chronic lymphocytic leukemia (CLL) and rare non-Hodgkin's B-cell subtypes such as hairy cell leukemia, Waldenström macroglobulinemia (WM), mantle cell lymphoma, and transformed NHL histologies
 - Hodgkin's lymphoma
- For Part 3 Expansion, Cohort B, subjects must have relapsed/refractory HL.
- For Part 3 Expansion, Cohort C, and Part 6, Cohort L, subjects must have relapsed/refractory DLBCL. Note: DLBCL subtype (eg, GCB) should be known at study entry.
- For Part 3 Expansion, Cohort D, subjects must have relapsed/refractory indolent lymphoma. Indolent lymphoma is defined as histologically confirmed follicular lymphoma Grade 1, 2, or 3a, or histologically confirmed marginal zone lymphoma.

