4.2.5. Crossover to Combination Therapy After Monotherapy Treatment

For subjects who discontinue INCB050465 monotherapy for a reason described in Section 5.7.1, the investigator may feel that the best option for the subject is to enroll in a combination therapy offered in this Protocol. Prior use of a PI3K inhibitor is not prohibited per the inclusion/exclusion criteria for combination cohorts. Therefore, subjects who discontinue INCB050465 may be allowed to cross over to combination therapy. In these cases, the subject must meet the eligibility criteria for the cohort they will cross over to, and the sponsor must approve the crossover.

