Diarrhea/colitis (\geq Grade 2)	Step 1: Interrupt INCB050465. Perform work-up for infection (including CMV, C. difficile , etc). Initiate or continue supportive care (see Section 5.6.2.1). Consider colonoscopy with biopsy for \geq Grade 3. Step 2: If infection is ruled out, start oral steroids, or consider IV steroids if subject is being given IV fluids. If no improvement with oral steroids, switch to IV steroids. When diarrhea resolves to \leq Grade 1, continue supportive care and taper steroids over 4 weeks. When taper is complete and diarrhea is \leq Grade 1, restart INCB050465 at next lower dose in consultation with the medical monitor. If \geq Grade 2 diarrhea reoccurs, permanently discontinue INCB050465.
Pneumonitis (Grade 1)	Step 1: Interrupt INCB050465 until the toxicity has resolved. Step 2: Restart INCB050465 at next lower dose. Monitor as clinically indicated.
Pneumonitis (Grade \geq 2)	Permanently discontinue INCB050465.
Skin toxicity (eg, rash, pruritus, etc, unless otherwise specified) (Grade 2-3)	Step 1: Interrupt INCB050465 until the toxicity has resolved to \leq Grade 1. Step 2: Restart INCB050465 at same dose. If assessed as related to INCB050465, restart at next lower dose in consultation with the medical monitor.
Exfoliative dermatitis (Grade 1)	Step 1: Interrupt INCB050465 until the toxicity has resolved. Step 2: Restart INCB050465 at next lower dose. Monitor as clinically indicated.
Exfoliative dermatitis (\geq Grade 2)	Permanently discontinue INCB050465.
Intestinal perforation (any grade)	Permanently discontinue INCB050465.
Pneumocystis jiroveci pneumonia infection	Interrupt INCB050465. Permanently discontinue INCB050465 if Pneumocystis jiroveci pneumonia infection is confirmed.
CMV infection	Subjects with CMV viremia without associated clinical signs of CMV infection should be carefully monitored. Consider interrupting INCB050465 for subjects with CMV viremia and clinical signs of infection until the infection has resolved. Restart INCB050465 reduced by 1 dose level if approved by the medical monitor.
Varicella zoster infection	Interrupt INCB050465. Restart INCB050465 only by approval of the medical monitor.
Any Grade 1 or 2 toxicity unless otherwise specified	Continue study drug treatment(s); monitor as clinically indicated.

Table 4: Guidelines for Interruption and Restart of Study Drug (Continued)

TOXICITY/NCI CTCAE GRADE	ACTION TAKEN

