5.6.3. Criteria for Permanent Discontinuation of Study Drug

The occurrence of unacceptable toxicity will require that the study drug be permanently discontinued. Unacceptable toxicity is defined as:

- Occurrence of an AE that is related to treatment with the study drug that, in the judgment of the investigator or the sponsor's medical monitor, compromises the subject's ability to continue study-specific procedures or is considered to not be in the subject's best interest.
- Toxicity requiring more than 2 dose reductions of INCB050465 or the combination of INCB050465 and INCB039110 or the standard therapy. Subjects enrolled in Part 6 who require > 2 reductions of the standard therapy may remain on INCB050465 monotherapy with medical monitor approval.
- Persistent toxicity requiring a delay of therapy for more than 2 weeks (14 days), except ALT/AST elevation, which may require 4 weeks (28 days) to resolve, unless approved by the medical monitor.
- Prolongation of QTc by > 60 milliseconds or to > 500 milliseconds confirmed by repeat ECG.
- Recurrent toxicity despite 2 dose reductions.

If study drug is permanently discontinued, the subject will be withdrawn from the study.

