5.7. Withdrawal of Subjects From the Study

5.7.1. Withdrawal Criteria

Subjects **must** be withdrawn from the study for the following reasons:

- Further participation would be injurious to the subject's health or well-being, in the investigator's medical judgment.
- The subject becomes pregnant.
- Consent is withdrawn.
- The study is terminated by the sponsor.
- The study is terminated by the local health authority or IRB or IEC.
- Unacceptable toxicity has occurred (see Section 5.6.2.1).
- Disease progression has occurred (see [Appendix D](#), [Appendix E](#), or [Appendix F](#) for definition) except
 - in the circumstance where, in the setting of otherwise stable disease, a medical procedure or radiation therapy is required to a single lesion, with medical monitor approval, or
 - if progression is observed on a once-weekly schedule after an objective response was observed on a QD schedule, a subject may be returned to the QD schedule if it is determined to be in the subject's best interest by the investigator (eg, no better

alternative) and agreed by both the subject and the medical monitor. The subject should be withdrawn when a subsequent radiological assessment demonstrates further deterioration or sooner based on clinical signs and symptoms.

- Note: Subjects receiving INCB039110 monotherapy study treatment may receive combination therapy with INCB039110 and INCB050465 as described in Section 4.2.

A subject **may** be withdrawn from the study as follows:

- If, during the course of the study, a subject is found not to have met eligibility criteria, the medical monitor, in collaboration with the investigator, will determine whether the subject should be withdrawn from the study. Refer to Section 11.3, Protocol Adherence.
- If a subject is noncompliant with study procedures or study drug administration in the opinion of the investigator, the sponsor should be consulted for instruction on handling the subject.

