5.7.2. Withdrawal Procedures

In the event that the decision is made to permanently discontinue the study drug, the subject will be withdrawn from the study and the end-of-treatment (EOT) visit should be conducted.

Reasonable efforts should be made to have the subject return for a follow-up visit. These visits are described in Section 5.10. The last date of the last dose of study drug will be recorded in the case report form (CRF), and the reason for subject withdrawal will be recorded.

If a subject is withdrawn from the study:

- The study monitor or sponsor must be notified.
- The reason(s) for withdrawal must be documented in the subject's medical record and in the CRF.
- The EOT visit should be performed.
- Subjects must be followed for safety until the time of the follow-up visit or until study drug-related toxicities resolve, return to baseline, or are deemed irreversible, whichever is longer.

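### Section 4.2.5 ties crossover to reasons that include toxicity requiring a permanent INCB050465 stop, and only incomplete default rules govern how crossover data are analysed

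*Protocol*

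**What the plan says.** **Who may cross over.** Section 4.2.5 of the protocol applies "For subjects who discontinue INCB050465 monotherapy for a reason described in Section 5.7.1". The investigator may then judge a combination in this protocol to be the best option. The subject must meet the eligibility criteria of the new cohort, and the sponsor must approve. The synopsis (Duration of Participation) is narrower: monotherapy subjects have the option of "crossing over to combination therapy upon progressive disease at the discretion of the investigator", provided a combination cohort is enrolling.

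**What 5.7.1 lists.** Progression is one reason among several. Another is "Unacceptable toxicity has occurred (see Section 5.6.2.1"). The section it points to is supportive care for diarrhea; unacceptable toxicity is defined in 5.6.3. Section 5.7.1 also carries a note: "Subjects receiving INCB039110 monotherapy study treatment may receive combination therapy with INCB039110 and INCB050465 as described in Section 4.2".

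**The stop rules.** Section 5.6.3 says: "The occurrence of unacceptable toxicity will require that the study drug be permanently discontinued". It adds: "If study drug is permanently discontinued, the subject will be withdrawn from the study", and 5.7.2 repeats this. Table 4 requires a permanent INCB050465 stop for Grade 2 or higher pneumonitis or exfoliative dermatitis, any intestinal perforation and confirmed *Pneumocystis* pneumonia. The same applies if ≥ "Grade 2 diarrhea reoccurs, permanently discontinue INCB050465". Section 4.1 confirms that INCB050465 is given in every part of the study.

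**Analysis.** In Section 9 of the protocol the word crossover appears only for the food-effect ANOVA, and the visible SAP text does not mention treatment crossover. General rules do reach these subjects; they are set out in the working below.

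**The concern.** A permissive rule and a mandatory rule meet on the same subjects, and no sentence says which prevails. A site that goes from 4.2.5 to 5.7.1 and follows the reference there lands on dietary and fluid advice for diarrhea, not on the stop rule. It could reasonably propose a combination containing INCB050465 for someone required to stop that drug permanently.

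The analysis question is separate. Safety is the primary endpoint and is reported by regimen. If combination-period events or tumor shrinkage are shown under monotherapy, or one person appears as two subjects in a total, the descriptive tables do not mean what their column headings say.

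**Working it through.** No arithmetic in the plan depends on crossover, so the check is mainly a comparison of texts.

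**1. Does 4.2.5 reach subjects under a permanent-stop rule?** Its trigger is the 5.7.1 list, which includes unacceptable toxicity. Under 5.6.3 that toxicity means permanent discontinuation. All combinations contain INCB050465. So the wording of 4.2.5 covers these subjects, while that of the synopsis does not.

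**2. Do the safeguards exclude them?** The relevant criteria in Section 3.3 are:
- Exclusion 2: no investigational drug within 28 days or 5 half-lives, whichever is longer, unless the medical monitor approves. Section 1.2.4 gives a half-life of about 8 to 12 hours, so 5 half-lives is 40 to 60 hours and the 28 days governs. This imposes a gap, not a bar.
- Exclusion 4: bars unresolved Grade 2 or higher toxicity. Resolved toxicity passes.
- Exclusion 17: prior PI3K inhibitor use is not excluded in the combination cohorts, as 4.2.5 itself notes.
- Exclusion 20 (serious medical condition) rests on investigator opinion, and exclusion 22 covers known hypersensitivity only.

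Example: a subject stops for Grade 2 pneumonitis, which resolves, and waits 28 days. Table 4 requires a permanent stop. None of these criteria excludes the subject automatically, so the decision falls to investigator judgment and sponsor approval.

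**3. What do the default analysis rules do if one record is kept?**
- Best overall response ends at the first progression (Protocol 9.4.2, SAP 7.2.2). Response rate is therefore protected after a crossover for progression, and exposed only after a crossover without it.
- Best lesion change is the largest decrease over the study, with no progression cut-off (Protocol 9.4.2, SAP 7.2.5). Shrinkage on the combination below the monotherapy nadir would enter the monotherapy waterfall plot.
- Data are grouped by the regimen first assigned (Protocol 9.4.1); SAP 5.2 says only dose groups. The AE window runs to 30 days after the last dose of study drug (SAP 8.1). Combination-period events would enter the monotherapy all-cause summaries.
- INCB050465 duration runs from Day 1 to its last dose (SAP 6.4), so it spans the washout and the combination period. Average daily dose uses that duration as its denominator.
- Baseline is set once, before any study treatment (SAP 4.1.3).

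**4. And if the subject re-enrolls?** Section 4.2.5 speaks of enrolling, 5.6.3 and 5.7.2 require withdrawal with an end-of-treatment visit, and 6.2 ties Cycle 1 Day 1 to enrollment and first dose. The text leans this way. The monotherapy windows then close at withdrawal, apart from the AE window: 30 − 28 = 2 days of possible overlap after the default washout. What remains is that one person can count twice in overall totals, and that nothing separates crossover subjects from newly enrolled combination subjects. Section 6.1 gives a new subject ID only for repeat screening after a screen failure, so it does not settle the matter.

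**The case against.** The strongest reply is that a permission does not cancel a mandatory stop. A site obeying both rules would not cross over a subject who must stop INCB050465. Section 4.2.5 is permissive throughout and carries two conditions. Section 5.6.2 describes its dose-reduction rules as guidelines, and Table 4 allows restart after some Grade 4 events with medical monitor approval, so sponsor review of re-exposure is already part of the plan. That is a fair account of the intent. It does not supply the missing sentence, and discretionary approval is weaker than the stop that 5.6.3 requires.

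A reader might infer that crossover is open after any 5.7.1 reason without limit. The documents do not support this: the list also contains withdrawn consent, pregnancy and study termination, and eligibility and sponsor approval always apply.

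A reader might also infer that the documents say nothing about how crossover data are analysed. That is too absolute. Grouping by initial regimen and the first-progression cut-off are defaults that apply. SAP Sections 7.2.3 and 7.2.4 are not visible, so absence can be claimed only for the text that is.

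The objection that contamination of monotherapy tables arises only on the one-record reading, and that the text favors re-enrollment, stands. It shrinks the analysis point without removing it. Causality is recorded per agent (Protocol 8.1.1) and INCB039110-related events have their own tables (SAP 8.2.3), so drug-related summaries are less exposed than all-cause ones. Dosing and events are listed by subject, which would let the periods be separated afterwards.

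**Conclusion.** The point holds in two parts.

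First, 4.2.5 is wider than the synopsis and overlaps with the permanent-stop rules. The safeguards narrow the overlap but do not bar a subject whose stop-rule toxicity has resolved.

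Second, the visible text has no crossover-specific analysis rule, and the defaults are incomplete. On one record, safety grouping, exposure and lesion change do not close at crossover. On re-enrollment, double counting and mixing with newly enrolled combination subjects remain.

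No size of bias can be stated, because the number of crossovers is not given. It is tempting to use the 11 of 46 subjects (24%) who had stopped for an AE by 02 SEP 2016 (Section 1.2.4). That figure counts AE discontinuations, without grades, and says nothing about how many met a stop rule or crossed over. Section 1.4.2 reports only 3 subjects on the INCB039110 combination at that date and does not say whether any had crossed over. The documents do not show that any subject was re-exposed against a stop rule or that any table is wrong.

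The study tests no hypothesis, so the stake is clarity of the safety rule and of the descriptive tables.

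**What to change.** **Protocol.** In 4.2.5, limit crossover to progressive disease, as in the synopsis. State that a subject who met a permanent-discontinuation criterion for INCB050465 in 5.6.3 or Table 4 may not cross over. Correct or delete the 5.7.1 note on INCB039110 monotherapy. Table 1 has no such cohort, but the synopsis text for Part 3 still mentions INCB039110 as a single agent, so the note may be a misnamed drug or a remnant of a dropped arm; the sponsor must say which. Point the toxicity reference in 5.7.1 to 5.6.3.

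**SAP.** Add a short paragraph that:
- ends monotherapy AE, exposure, response and lesion-change data at the first combination dose;
- sets a new baseline from that dose;
- shows crossover subjects separately from newly enrolled combination subjects;
- counts each person once in overall totals.

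**Cost.** A few sentences in each document, some extra programming and no new data collection. Fewer subjects could cross over. With Amendment 10 reducing procedures for ongoing subjects, the protocol edit has little prospective effect. The SAP paragraph matters more for what is reported: the SAP was written for Amendment 3, declares itself effective for later amendments (SAP 2.1), and lists only its original version (SAP Table 5).

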4.3. Study Endpoints

[figure not shown]
4.3.1. Primary Endpoint

- Safety and tolerability of the planned study treatments as assessed by summary of AEs, clinical laboratory assessments, physical examination results, and 12-lead ECGs.

4.3.2. Secondary Endpoints

- Efficacy as measured by ORR, defined as the sum of subjects achieving a minor response (MR, only among subjects with WM), PR, very good partial response (VGPR, only among subjects with WM), and CR to the planned study treatments based on:
 - International Workshop on Chronic Lymphocytic Leukemia (IWCLL) criteria for CLL ([Hallek et al 2008](#), [Cheson et al 2012](#)).
 - Vth International Workshop on Waldenström macroglobulinemia response assessment for subjects with Waldenström macroglobulinemia ([Owen et al 2013](#))
 - Revised response criteria for lymphoma for HL and NHL ([Cheson et al 2014](#)).
- C_{max} , T_{max} , C_{min} , AUC_{0-t} , and $AUC_{0-\tau}$ at Cycle 1 Day 15 of INCB039110 in combination with INCB050465.

- C_{\max} , T_{\max} , C_{\min} , AUC_{0-t} , and $AUC_{0-\tau}$ of INCB050465 as monotherapy and in combination with INCB039110.

4.4. Measures Taken to Avoid Bias

This is an open-label study; no comparisons will be made between subjects or against historical controls. Measurements of safety and efficacy are objective measurements and only comparisons to pretreatment conditions will be made.

4.5. Number of Subjects

Up to approximately 150 subjects are planned for enrollment at approximately 15 sites. The number of subjects may vary due to the number of cohorts required to determine the tolerated or recommended dose.

4.6. Study Termination

If a PAD (eg, trough plasma concentration of $\geq IC_{90}$) cannot be reached in a cohort with less than one-third of the subjects experiencing a DLT as monotherapy or combination therapy, the study will be terminated.

The sponsor may terminate the study electively or if required by regulatory decision. If the study is terminated prematurely, the sponsor will notify the investigators, the institutional review boards and independent ethics committees (IRBs/IECs), and regulatory bodies of the decision and the reason for termination of the study.

The investigator retains the right to terminate study participation at any time, according to the terms specified in the study contract. The investigator is to notify the IRB or IEC in writing of the study's completion or early termination, and send a copy of the notification to the sponsor or sponsor's designee and retain 1 copy for the site study regulatory file.

5. TREATMENT OF SUBJECTS

5.1. Treatment Groups and Administration of Study Drug

5.1.1. INCB050465 Monotherapy

Subjects will self-administer INCB050465 using an oral daily QD, BID, or intermittent regimen, as instructed by the investigator. INCB050465 should be administered in the clinic on Days 1, 8, and 15 of Cycle 1. Subjects enrolled in Part 3 Cohort A participating in the food-effect study will also have INCB050465 administered in clinic on Cycle 2 Day 1. INCB050465 will be taken orally with water without regard to food. If QD or once-weekly intervals are used, INCB050465 should be taken at approximately the same time each day.

5.1.2. INCB050465 and INCB039110 Combination Therapy

In Part 2 and Part 3 (Cohort E), subjects will concomitantly receive INCB039110 (administered QD) with INCB050465. INCB050465 and INCB039110 should be administered in the clinic on Days 1, 8, and 15 of Cycle 1. INCB039110 will be given after all INCB050465 PK sampling is complete on Day 1. At other designated visits where INCB039110 is administered at the site, it can be given with INCB050465. For either drug, if a dose of is missed, the subject should skip the dose and take the next scheduled dose at the usual time.

If BID doses are used, INCB050465 should be taken morning and evening, at approximately 12-hour intervals. For QD administration, if a dose is missed by more than 12 hours, the subject should skip the dose and take the next scheduled dose at the usual time. For BID administration, if the morning or evening dose is missed by more than 4 hours, the subject should skip that dose and take next scheduled dose at the usual time. For once-weekly dosing, if the dose is missed by more than 2 days, the subject should skip the dose and take the next scheduled dose.

One cycle will be defined as 21 days of treatment; subjects will receive treatment in continuous cycles. All subjects will attend study visits weekly during the first cycle, and at the beginning of each 21-day cycle thereafter.

